8.8.6 PHOTOGRAPHIC READING CENTER

The Reading Center for grading of conjunctival photographs will be based at the Proctor Foundation. Three graders will independently grade each photograph, masked to treatment allocation. We will choose the consensus or median grade for all outcomes. We will assess inter- and intra-observer agreement with kappa statistics.

Facility/Equipment. A dedicated room with a single 24" computer monitor (1920 x 1200 pixels, re-calibrated monthly to a color temperature of 6500 Kelvin and 2.2 gamma) will be used to grade photographs. Full-screen photographs will be read at 26 inches with the shades drawn and lights off.

Naming Conventions. The PNSO study coordinator will be responsible for renaming each of the photographs taken during the study. The naming convention to be used is that the file will be a concatenation of the 6-digit random number, then the study visit (0, 36), and then the photograph number from that visit. For example, if a child with random number 111999 had 3 photographs taken at the 36-month visit, these 3 photographs would be relabeled as 111999-36-1, 111999-36-2, and 111999-36-3.

Photograph Selection and Arrangement. The best quality conjunctival photograph will be selected from each participant and displayed in a PowerPoint slide (left=month 0; right=month 36). The random number will be added to each PowerPoint slide for identification purposes. The best photograph will be pre-selected but the photographic graders will have access to all other photographs taken of the study participant in a folder on the computer; they simply navigate to the correct file name using the naming conventions listed above.

8.9 DRIED BLOOD SPOTS COLLECTION

A random sample of 40 children 1-9 years old will undergo dried blood collection at 0 and 36 months. The dried blood spots will be processed for *C. trachomatis*. Samples will be processed within in pools of 5. Any positive pools will be unpooled and processed individually. Swabs will be labeled with a unique barcode in the field, which will link to a unique identification number. The number will be linked with the individual's census entry during swab collections in the field.

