9.2.3 PROCEDURE FOR POOLING SAMPLES

We will increase the efficiency of chlamydial testing by combining swabs from the same age stratum and same community into pools of 5 random swabs for processing. An internal control will be run with each pool to rule out the possibility of PCR inhibitors. Any inhibitory pools will be re-tested, and if still inhibitory, the swabs will be individually re-tested. If PCR from any pool is equivocal, then all swabs from the pool will be tested individually. While samples will necessarily be diluted in this process, this is not thought to affect the sensitivity of the test. We will unpool all positive pools in the ages 1 month – 9 years age stratum and estimate the community prevalence of chlamydial infection as the proportion of positive swabs. We will estimate the community prevalence of infection in the ≥ 10 year age strata using maximum likelihood estimation, similar to our previous trials: the number of individual swabs with the maximum likelihood of having resulted in the observed pooled results will be chosen as the estimate for that village.

In order to pool the conjunctival samples in the lab, the microbiology lab staff will assign a new pool ID number for every sample, and samples will be stored at -80°C freezer until PCR testing (if not processed that day).

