14.7 ESTIMATION OF DISEASE PREVALENCE

Computerized randomization is utilized to prepare samples for pooling. PCR pooling will be conducted stratified by study community. All samples will be pooled in pools of 5. We will automatically unpool any positive pools results tabulated by development team.

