Inflammation and active trachoma (TF, TI) as measured by conjunctival photography are dichotomous variables at the individual level, and will yield community-level averages analogous to the primary outcome. The analysis will follow the same methods as described for the primary outcome.

Seropositivity to chlamydia will be measured from dried blood spots, including antibody responses to the antigens Pgp3 and CT694. We will dichotomize antibody responses based on

seropositivity cutoffs established through receiver-operating characteristic (ROC) curve analyses of known positive and negative specimens (conducted at the CDC WHO reference center for trachoma serology). Seropositivity at the individual level will be a dichotomous variable yielding a community-level average of seroprevalence. We will estimate seroprevalence separately by antigen and using the combined response. We will analyze two populations for serologic endpoints. At the community level, we will analyze seroprevalence among children aged 12–36 months (only those born during the duration of the trial) to assess exposure to ocular chlamydia during the study period using a model identical to the primary outcome model. We will also analyze individual-level seropositivity data in the entire age range (1–9 years for serologic measurements) to assess age-seroprevalence curves in children in continuation versus stopping communities. We will additionally estimate the seroconversion rate as measure of force of infection using age-structured seroprevalence using a generalized linear model with a complementary log-log link, age as an offset and treatment arm as a covariate. Since this is an individual-level analysis (rather than community-level), we will estimate standard errors for the model using robust, Huber-White standard errors clustered at the community level.

The trial does not currently include prespecified subgroup analyses.

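### Protocol 8.9 applies the swab PCR pooling rule to dried blood spots, with no pool cutoff or pooled sensitivity to support the SAP's per-child serology

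*Protocol*

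**What the plan says.** Protocol 8.9 sets the blood sample: "A random sample of 40 children 1-9 years old will undergo dried blood collection at 0 and 36 months". It then gives the testing rule: "Samples will be processed within in pools of 5. Any positive pools will be unpooled and processed individually". The next sentence is still about swabs: "Swabs will be labeled with a unique barcode in the field, which will link to a unique identification number". Protocol 8.7, on conjunctival swabs for PCR, contains the same pooling sentences word for word.

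The detailed pooling procedure in Protocol 9.2.3 concerns swabs only: "combining swabs from the same age stratum and same community into pools of 5 random swabs for processing". On dilution it says: "While samples will necessarily be diluted in this process, this is not thought to affect the sensitivity of the test". Protocol 14.7 reads: "PCR pooling will be conducted stratified by study community. All samples will be pooled in pools of 5".

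Protocol 4.3 makes clear that the blood spots are for serology, and Protocol 2.2.2 lists seropositivity to Pgp3 and CT694 as a secondary outcome. SAP 6.2.1 (Aim 1) dichotomises antibody responses at cutoffs from ROC analysis of known positive and negative specimens, for each antigen and for the combined response. It continues: "Seropositivity at the individual level will be a dichotomous variable yielding a community-level average of seroprevalence". It also plans individual-level age-seroprevalence curves and a seroconversion model over ages 1 to 9 years.

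**The concern.** Protocol 8.9 is the only protocol text on how the blood spots are tested. Section 9 describes swab PCR, and nothing in it covers an antibody assay. A laboratory working from the protocol would therefore pool the spots.

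Pooling is a reasonable economy for PCR, where the target is amplified. An antibody reading has no such step, so mixing one positive spot with four negatives may pull the reading below a cutoff set for individual specimens. The whole pool would then be called negative and the positive child never retested.

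A weak positive in such a pool is recovered only if a pool-mate makes the pool positive. Sensitivity would then depend on local seroprevalence and could differ between communities, arms and visits. What is exposed is the secondary serology comparison, including the community-level analysis in children aged 12–36 months, and the hidden Markov model of Aim 2, which takes both antibodies as inputs.

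**Working it through.** The plan gives no figure to reproduce. The check sets the two documents side by side, then works out what the written rule would do under stated assumptions.

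**Inputs from the documents.** Pool size 5; 40 children per community per visit; 80 communities (Protocol 2.3.3); between-community SD of seroprevalence 0.15 and detectable margin 6.9 points (SAP 3.3.1).

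**Assumptions, not in the documents.** Seroprevalence *p*; background signal of a negative spot, *b* times the cutoff; share *w* of positives weak enough to be missed when alone in a pool; linear averaging of signal; the individual cutoff applied unchanged to the pool.

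**1. What the SAP needs and what the protocol supplies.**

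| Needed for pooled serology | Protocol | SAP |
|---|---|---|
| Cutoff for a pool | not given | not given; cutoffs come from known specimens |
| Antigen that triggers unpooling | not given | not given; each antigen and the combination are analysed |
| Sensitivity after dilution | addressed for swab PCR only (9.2.3) | not given |

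**2. Does every child get a status?** Yes. Positive pools are retested individually and members of negative pools are called negative. With a fully sensitive pool test, simulated agreement with true status was 100%. What is lost is the antibody level of children in negative pools, and the SAP's stated serology analyses use dichotomised status.

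**3. Dilution.** A lone positive at *L* times the cutoff reads (*L* + 4*b*)/5 and is missed if *L* < 5 − 4*b*. For *b* = 0, 0.1, 0.25 and 0.5, the threshold is 5.0, 4.6, 4.0 and 3.0 times the cutoff.

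**4. How often a positive child is alone in the pool.** If all communities share the same *p*, the probability is (1 − *p*)^4: 0.95^4 = 81%, 0.90^4 = 66% and 0.80^4 = 41% at *p* = 5%, 10% and 20%. Pools are formed within a community, so clustering lowers this. With a beta distribution (an assumption) and the SAP's SD of 0.15, the shares at the same means are 19%, 32% and 29%. With SD 0.10 they are 42%, 47% and 35%.

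**5. Effect on the arm difference.** Suppose weak positives are missed only when alone. At common *p*, observed seroprevalence is *p*[1 − *w*(1 − *p*)^4]. Its slope in *p* is 1 − *w*(1 − *p*)^3(1 − 5*p*), which is below 1 when *p* < 20% and above 1 beyond that. For a true difference of 6.9 points:

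| Lower-arm seroprevalence | *w* = 0.1 | *w* = 0.3 |
|---|---|---|
| 5% | 6.6 | 6.0 |
| 20% | 7.0 | 7.1 |

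The difference shrinks at low prevalence and is slightly enlarged from 20% upward.

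**6. Number of tests.** Individual testing is 80 × 40 = 3,200 samples per visit. Under the written rule there are 3,200/5 = 640 pools plus retests, so tests per child are 0.2 + 1 − (1 − *p*)^5. This gives 0.43, 0.61, 0.87 and 1.03 at *p* = 5%, 10%, 20% and 30%.

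**The case against.** The best defence is that this is copied text, not a chosen assay design. The sentences match 8.7 exactly, 8.9 goes on to speak of swabs, and the working procedure in 9.2.3 never mentions blood. That is very likely true. It explains the wording but does not remove it, because no other protocol text tells the laboratory how to test the spots.

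Four stronger readings are tempting, and the documents do not support them:

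- *Pooling cannot yield individual seropositivity.* It can (step 2). The gap is that correct status cannot be relied on while no pool cutoff is defined.
- *Protocol 14.7 confirms that blood is to be pooled.* The sentence "All samples will be pooled in pools of 5" follows directly on one about PCR pooling, so it most naturally means PCR samples. It is ambiguous, not corroboration.
- *Weak positives will be lost in large numbers.* The documents describe neither the assay's signal nor its background, do not say that an individual cutoff would be used on a pool, and give no share of positives below 5 times the cutoff. The 81% lone-positive share also requires equal seroprevalence everywhere, which does not fit the SAP's SD of 0.15.
- *The error favours noninferiority.* Under the simple model that holds only below about 20% seroprevalence, and the documents state no expected level.

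It is also fair to say that pooling would save real work at low prevalence: at 5%, individual testing is 1/0.43, or about 2.3 times as many assays.

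**Conclusion.** The point stands as a conflict between Protocol 8.9 and the SAP's serology methods that should be corrected before the spots are tested. The rule as written lacks what a pooled antibody test would need, and the protocol's reassurance on dilution does not reach it.

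The possible harm is missed weak positives. It depends on linear averaging, on the individual cutoff being used for pools, and on how many positives are weak. For illustration, at a common seroprevalence of 5% with 10–30% of positives weak, 0.81 × 10% to 0.81 × 30%, or 8–24% of positives, would be lost. At 20% the loss would be 0.41 × 10% to 0.41 × 30%, or 4–12%. Clustering between communities would change these figures, and at a mean of 5% it would lower them substantially. They are not estimates for this trial.

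The consequence is confined to secondary serology and Aim 2. The primary outcome, ocular chlamydia by PCR on swabs, is unaffected.

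**What to change.** In Protocol 8.9, delete the two pooling sentences and state that each dried blood spot is tested individually for Pgp3 and CT694 antibody against the reference-centre cutoffs named in the SAP. Replace the references to swabs in that section with dried blood spots. In Protocol 14.7, say that pooling applies to conjunctival swabs for PCR.

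If pooling of blood spots is in fact intended, the documents should instead give, for each antigen, a validated pool cutoff, its sensitivity and the rule that triggers unpooling.

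The edit is a change of protocol wording. Laboratory work is 3,200 samples per visit. Under pooling it would be about 1,360 tests at an assumed seroprevalence of 5% (3,200 × 0.426) and about 2,790 at 20% (3,200 × 0.872); at about 30% pooling saves nothing. Relative to the SAP, which is already written around each child's own antibody result, the added burden is small.

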8.9.1 PROTOCOL FOR COLLECTION

Materials Needed.

FTA Elute cards
Small zip plastic bags
Desiccant packs

Masking tape

Large Ziploc bags (handful)

TropBio circular cards

Materials for drying apparatus: 12 sharpened pencils, Styrofoam, empty cardboard box

Procedures.

Fingerstick. Inform the mother that her child's finger will be pricked to obtain blood. Describe the finger prick procedure, reassure her, and answer all questions. The blood specimen should be collected as described below to minimize the discomfort of the child and to ensure sufficient blood volume collection.

A finger stick of capillary blood will be collected for dried blood spots to be stored for later testing. Blood will be collected by a gloved health worker using aseptic technique. Gloves will be changed between each participant. The fingerprick or heelstick site will be disinfected using a 70% isopropyl alcohol swab.

Fingerstick procedure:

1. Prepare the disposable lancet. Use a NEW disposable lancet for each child. Do not re-use lancets!
2. The recorder will scan the child's QR code, and place a random number sticker on the TropBio filter paper and the (right edge of the) slide.
3. Position the child for the finger stick. Make sure that the child's right hand is warm and relaxed. Hold the child's thumb, middle, or ring finger on his/her right hand (from the top of the knuckle to the tip of the finger) between your left thumb and finger and disinfect in small outward circles with an individually packaged alcohol wipe.
4. After the alcohol dries, use the thumb to lightly press the child's thumb or finger from the top of the knuckle towards the fingertip to stimulate blood flow towards the sampling point (puncture site). For the best blood flow and least pain, prick the side of the thumb/fingertip, not the center. While applying light pressure towards the thumb/fingertip, hold the lancing device in your hand and prick the thumb/finger. If the finger prick is performed properly, a single prick should be sufficient to collect the required amount of blood.
5. Allow the blood to ooze out. Wipe away the first 2 or 3 drops of blood with gauze. If necessary, re-apply light to moderate pressure towards the thumb/fingertip (approximately 1 cm behind the site of the finger prick) until another drop of blood appears.

Note: Do not squeeze forcefully. Avoid "milking" as it may dilute the blood with tissue plasma.

[figure not shown]
Collection.

Collecting the FTA Elute filter paper sample:

1. Label the filter paper with a random number sticker.
2. Place 2-4 large drops of blood directly from the thumb or finger onto the large circle on the filter paper (if it is difficult to obtain 4 drops of blood, it is sufficient to collect 2 drops of blood).
3. Leave the filter paper to air dry for a few minutes, then place the sample into a small plastic bag along with a desiccant packet.
4. Leave the bag open for a few minutes more, and when the blood is **completely** dry, roll down the top of the bag and close with a piece of masking tape.
5. Store the filter paper samples (in small plastic bags) in a larger Ziploc bag. Keep all filter paper samples in a safe, dry place at room temperature.
6. Blood spots will be stored at room temperature in a locked cabinet in the study coordinators' office.

Collecting the TropBio filter paper sample:

1. Label the filter paper with a random number sticker.
2. Grip the filter paper on the side without small circles. Place a droplet of blood directly from the thumb or finger onto five of the six circles, leaving the right one blank. Be sure to fill each circle completely.

Leave last circle blank

Area to hold the filter paper.
Do not touch the small circles.

3. The recorder will scan the QR code.
4. Carefully slide the filter paper onto a pencil to air dry for at least an hour. There should be about 1 cm in between each sample. Secure the pencil into a Styrofoam surface in a box or container to protect from dust.
5. When the filter paper is dry, place each sample into a small zip plastic bag (individually). Place the small bags into a larger Ziploc bag with five desiccant packets.
6. Ensure the large Ziploc bag is sealed tightly, as moisture will damage the samples. Transport these filter paper samples to a freezer.

Set-up drying area for TropBio bloodspots.

Supplies: pencils, Styrofoam, cardboard box, paper

- Place Styrofoam in cardboard box
- Put pencils in box/container – space apart
- *Note:* When placing the blood spot samples on the pencil, space apart by ~2.5cm with pieces of paper in between each sample.

9. MICROBIOLOGY LAB PROCEDURES

9.1 MICROBIOLOGY PROCEDURES

Samples will be collected with reference to age, gender, household, and study cluster, but participant names will not be included in laboratory records. Samples will thus not be associated with the individual's name, but with a 6-digit random identification number, masking laboratory personnel and preventing identification of the individuals infected. For outcome assessment, laboratory results will not be available for weeks if not months.

9.2 METHODS

Laboratory testing is the current standard of care of identification of *C. trachomatis* infections in the United States. After collection, all samples will be processed in the Ralph and Sophie Heintz Laboratory at the Proctor Foundation in San Francisco and will be filled with 1 mL of M4RT media, and testing for *C. trachomatis*.

Swabs will be processed with the Abbott RealTime assay for *Chlamydia trachomatis*, using the automated Abbott m2000 System. The RealTime assay targets the cryptic plasmid of *C. trachomatis*. The assay has been shown to be highly sensitive and specific for the diagnosis of sexually transmitted *C. trachomatis*, with sensitivities exceeding that of the nucleic acid amplification test used in most recent trachoma studies (Roche AMPLICOR).

9.2.1 PROCESSING OF SAMPLES FOR PCR

Samples are handled as per Abbott RealTime sample processing protocol, with the following modifications:

1. Samples are boiled for 10 minutes at 100°C. Boiling of samples is an accepted treatment method to remove substances that may be inhibitory to the PCR amplification process.
2. Samples are pooled.

9.2.2 PROCEDURE FOR MASKING SAMPLES

In order to mask the location origin, the control status, and the clinical exam grading of the conjunctival samples collected in the field, the Database Manager will assign an identification number different from the random number assigned to each child. The PCR results will be recorded according to this laboratory identification number, thus masking the lab until all the samples have been processed. The Database Manager will then link the lab ID number to the random sample number to reveal the test results by development team.

9.2.3 PROCEDURE FOR POOLING SAMPLES

We will increase the efficiency of chlamydial testing by combining swabs from the same age stratum and same community into pools of 5 random swabs for processing. An internal control will be run with each pool to rule out the possibility of PCR inhibitors. Any inhibitory pools will be re-tested, and if still inhibitory, the swabs will be individually re-tested. If PCR from any pool is equivocal, then all swabs from the pool will be tested individually. While samples will necessarily be diluted in this process, this is not thought to affect the sensitivity of the test. We will unpool all positive pools in the ages 1 month – 9 years age stratum and estimate the community prevalence of chlamydial infection as the proportion of positive swabs. We will estimate the community prevalence of infection in the ≥ 10 year age strata using maximum likelihood estimation, similar to our previous trials: the number of individual swabs with the maximum likelihood of having resulted in the observed pooled results will be chosen as the estimate for that village.

In order to pool the conjunctival samples in the lab, the microbiology lab staff will assign a new pool ID number for every sample, and samples will be stored at -80°C freezer until PCR testing (if not processed that day).

9.2.4 QUALITY CONTROL

- 1) A *C. trachomatis*(+) control and a *C. trachomatis*(-) control (targeting 136 base pairs of a pumpkin gene) is included in each test run of the Abbott RealTime assay.
- 2) To test the effect of sample processing, a known positive sample is processed and tested in each test run. (This control is helpful when testing large numbers of negative samples.)
- 3) An internal control intended to identify specimens that contain polymerase inhibitor is run routinely on each sample. The internal control helps identify false negative results.

9.2.5 QUANTIFICATION

For every individual who tests positive for chlamydia, we will also run PCR for the beta actin gene on the same sample, in order to normalize the quantity of chlamydial DNA to the amount of the specimen. Quantitative results from the Abbott system are given in terms of a decision cycle (DC) number. We will generate a ratio of the DC number of the chlamydial DNA to the DC number of the beta actin gene and use the resulting ratio as the chlamydial load.

9.2.6 LABORATORY RESULTS REPORTING

All lab results will be kept in computer files as well as in hard-copy form by the Database Manager. The principal investigators and the DSMC will be updated regularly on the progress of the lab work throughout the course of the study.

